## II. Objectives

### A. Primary objectives:

1. Studies in tissue: The primary objective of this study will be to determine associations between PD-L1 expression (quantitatively determined as a continuous variable) in tumor tissue at baseline and an objective response to protocol treatment.
2. Peripheral blood studies: To determine association between changes in percentages of circulating activated T-cells, specifically CD8+/HLA-DR+/Ki-67+ T cells and an objective response to protocol treatment.

B. Exploratory studies

1. To associate levels of tumor infiltrating CD8+ T-cells, and PD-L1 expression defined categorically, and also in specific cell populations such as tumor cells and tumor infiltrating lymphocytes with response
2. As tissue allows, to explore correlations between response and multiple immunologic biomarkers including PD-1, CTLA-4, MHC-1, MHC-2, Lag-3, B2M, Na channel and other exploratory multiplex IF to determine expression levels of these biomarkers in components of the tumor microenvironment and in relation to each other
3. To evaluate mechanisms of resistance by comparing immunologic markers in sequential biopsies and biopsies taken at progression if available
4. To explore correlations between PD-L1 expression and CD8 + T-cell tumor infiltration with overall tumor mutational burden as determined by whole-exome and targeted sequencing to be performed through the parent NCI MATCH study
5. To explore associations between changes in a panel of circulating immune populations and immunologic cytokines with response Methodology

III. **Methodology**

Summary:

Correlative science will involve immune evaluation of archival tissue, serum and PBMCs obtained from multiple time points. PD-L1 expression and CD8+ T-cell infiltration will be evaluated on cut FFPE slides as below to correlate with response. We will also examine changes in these biomarkers over time when sequential biopsy specimens are available. Additional tissue, when available will be used for multiplexed IF and assayed for other immunologic markers as described in detail below. CyTOF will primarily examine changes in circulating activated T-cells over the course of therapy as a predictor of response but will also explore other immune subsets and cytokines.

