## IV. Statistical Considerstions

### A. Endpoints

1. Primary
  - a) PD-L1 positivity
  - b) Percent of circulating, activated CD8+/HLA-DR+/Ki-67+ T-cells
2. Secondary
  - a) PD-L1 positive cases

- b) Infiltration of lymphocytes per high powered field
- c) Exploratory analyses of expression levels of various serum cytokine and tumor immune biomarkers

B. Case selection and Sample Size

All consenting cases with adequate biospecimen available from the Z1D subarm.

Sample size estimate: 44 patients for tissue analyses, 37 patients for blood analyses

C. Analysis plan:

Regarding the primary endpoint of PD-L1 expression in tumor tissue, an unpaired t test will be used to compare the percent positive tumor cells in responders vs. non-responders. Responders will be determined using the primary endpoint of the trial – objective tumor response. Using the data provided in the supplementary appendix to Le et al. as a basis for the power calculations (Le DT, Uram JN, Wang H, et al. PD-1 blockade in tumors with mismatch-repair deficiency. N Engl J Med 2015;372:2509-20) it is assumed that PD-L1 expression, measured as a percentage of positive cells, will have a mean percentage of roughly 20% and a standard deviation of about 10%. Using these figures and assuming also that roughly 24% of all patients in this subarm will be responders, with approximately 44 patients with tissue available (roughly 11 responders and 33 non-responders) there is at least 80% power to detect a mean difference of 10% (e.g., 29% versus 19%) in PD-L1 expression between responders and non-responders using a two-sided 0.05 level t-test. The 24% figure used for the calculations was chosen based on the results of this arm recently presented at SITC.

Given the small sample size of this subarm, a categorical analysis to correlate objective response with PD-L1 positivity (for example via Fisher's exact test using a 5% cutpoint for PD-L1 positivity) will not have meaningful power, hence the proposed analyses will be done on the continuous PD-L1 metric and any categorical analyses will be considered exploratory. Following the logic of the power analyses above, there is 80% power to detect a 1.00 standard deviation difference in the means of any quantitative biomarker between responders and non-responders (assuming the overall response rate above) using a two-sided 0.05 level t-test.

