The primary endpoint of studies to be conducted on peripheral blood will evaluate changes in percentage of circulating CD8+/HLA-DR+/Ki-67+ T cells and response. We will compare the change in percentage of this cell population between responder and non-responder patients. To give a sense of power for studies to be done on paired tissue and blood samples (baseline versus progression), and blood samples (paired within patient comparing baseline vs progression) for analyses of various quantitative biomarkers being proposed here, differences will be taken for all measures and the hypotheses is that biomarkers will change (increase or decrease) post therapy. PD-L1 expression on tumor cells, infiltrating and circulating T-cell populations, myeloid derived suppressor cells, and immunologic cytokines and other immunologic markers. Assuming that within this cohort we will obtain paired samples on conservatively 40 patients, using a two-sided 0.05 level paired t-test there is at least 80% power to detect a 0.46 SD change in mean of a quantitative correlative parameter using a two-sided test with 5% type I error. Quantitative measure will be transformed to attain normality or appropriate non-parametric tests will be conducted. With this level of consent for these studies in this cohort there is sufficient power for meaningful analyses. Power for these tests will be further improved if a greater percentage of the cohort of 47 patients consent and provide post-baseline (progression) samples for analysis.

D. Rationale for the sample size estimate:

As described above, assuming that roughly 24% of all patients in this subarm will be responders, with 44 patients (expected distribution to be roughly 11 responders and 33 non-responders) there is at least 80% power to detect a mean difference of 10% (e.g., 29% versus 19%) in PD-L1 expression between responders and non-responders using a two-sided 0.05 level t-test.

For the blood studies, assuming approximately 40 patients have usable specimens pre and post treatment, using a two-sided 0.05 level paired t-test there is at least 80% power to detect a 0.46 SD change in mean of a quantitative correlative parameter using a two-sided test with 5% type I error.

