We propose to evaluate associations with PD-L1 expression measured as a continuous metric of positivity (as described above) as opposed to a single cutoff. Exploratory analyses will assess specific cutpoints of PD-L1 positivity (e.g. 1%, 5%, 10%, etc.) as potential biomarkers, as these cutpoints have been described previously in the literature. To our knowledge there are unfortunately no on-treatment pathologic specimens available and therefore magnitude of change on treatment cannot be assessed. As mentioned in the above statistical analysis plan, assuming that within this cohort we will obtain paired samples on conservatively 40 patients that yield evaluable data for our flow-cytometric biomarkers, using a two-sided 0.05 level paired t-test there is at least 80% power to detect a 0.46 SD change in mean of a quantitative correlative parameter using a two-sided test with 5% type I error. Quantitative measures will be transformed to attain normality or appropriate non-parametric tests will be conducted as appropriate. We will also compare changes between responder and non-responder groups for the purpose of our analyses.

E. Statistical considerations for secondary objectives (if applicable)

Our secondary objectives for testing multiple biomarkers in tissue and serum are exploratory. However, these objectives are based on strong biologic rationale

and may also identify future targets for combinations with PD-1 inhibitors in patients with mismatch repair deficiency or other tumors.

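### Appendix V gives two blood sample sizes (37 and 40), and its blood power figure is for an overall pre/post change, not for the planned responder versus non-responder comparison

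*Protocol*

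**What the plan says.** All of this is in Protocol Appendix V (CS-MATCH-0005).

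- **Objective (II.A).** The primary peripheral blood objective is "To determine association between changes in percentages of circulating activated T-cells", specifically CD8+/HLA-DR+/Ki-67+ cells, and objective response.
- **Sample size (IV.B).** "Sample size estimate: 44 patients for tissue analyses, 37 patients for blood analyses".
- **Planned blood analysis (IV.C).** "We will compare the change in percentage of this cell population between responder and non-responder patients". The same paragraph then turns to paired samples, where "the hypotheses is that biomarkers will change (increase or decrease) post therapy". It gives at least 80% power for a 0.46 SD change with 40 pairs, using a two-sided 0.05 paired t-test.
- **Rationale (IV.D).** The blood figure is repeated: "For the blood studies, assuming approximately 40 patients have usable specimens pre and post treatment, using a two-sided 0.05 level paired t-test". Later in IV.D it appears again: "we will obtain paired samples on conservatively 40 patients that yield evaluable data for our flow-cytometric biomarkers". A closing sentence adds "We will also compare changes between responder and non-responder groups for the purpose of our analyses", with no power or detectable difference attached.
- **General two-group statement (IV.C).** After the tissue calculation (44 patients, 11 responders and 33 non-responders), the plan says "there is 80% power to detect a 1.00 standard deviation difference in the means of any quantitative biomarker between responders and non-responders".

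**The concern.** There are two mismatches. First, the number of patients with both a pre and a post specimen cannot exceed the number in the blood analyses, so 40 pairs cannot be a conservative assumption beside an estimate of 37.

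Second, and more important, the paired t-test asks whether the marker moves on average over all patients. The primary blood objective asks whether the movement differs between responders and non-responders. That is a comparison of two independent, unequal groups, and the smaller one would have about 9 or 10 patients. For tissue, IV.D gives a responder versus non-responder difference; for blood it gives only the overall change.

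A reader who takes 0.46 SD as the sensitivity of the blood study would overrate it by more than a factor of two, and could read a null result on the primary blood question as stronger evidence than it is.

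**Working it through.** **Inputs from Appendix V.** Blood n = 37 (IV.B) or 40 pairs (IV.C, IV.D); 0.46 SD, two-sided 0.05, paired t-test (IV.C, IV.D); 24% responders and a tissue split of 11/33 (IV.C).

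**Assumptions for the blood comparison, which the protocol does not state.** The 24% share also holds among patients with paired blood; the test is an unpaired t-test on the change; the SD of the change is the same in both groups. SD in the two-group blood results means the SD of the change.

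Power is from the exact noncentral t distribution, two-sided 0.05.

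**1. The plan's paired figure.** Noncentrality = d × √n, df = n − 1.

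| n | d (SD) | Noncentrality | Power |
|---|---|---|---|
| 40 | 0.46 | 0.46 × √40 = 2.909 | 81.0% |
| 39 | 0.46 | 2.873 | 79.9% |
| 37 | 0.46 | 2.798 | 77.7% |
| 37 | 0.47 | 2.859 | 79.4% |
| 37 | 0.48 | 2.920 | 81.1% |

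The stated figure reproduces at 40, which is the smallest n that reaches 80%. At 37 the effect has to be restated as 0.48 SD (to two decimals) to keep at least 80%.

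**2. The plan's two-group figure.** Noncentrality = d × √(n1·n2/(n1+n2)), df = n1 + n2 − 2. For tissue, 11/33 at 1.00 SD: √(11 × 33/44) = 2.872, power 80.1%. This also reproduces.

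**3. The planned blood comparison.** Expected responders: 0.24 × 37 = 8.9, so 9/28; 0.24 × 40 = 9.6, so 10/30.

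| Split | √(n1·n2/(n1+n2)) | Power at 0.46 SD | Power at 1.00 SD | Detectable with 80% power |
|---|---|---|---|---|
| 9/28 (n = 37) | 2.610 | 21.5% | 71.8% | 1.10 SD |
| 10/30 (n = 40) | 2.739 | 23.3% | 76.1% | 1.05 SD |

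For 9/28 the solution is 1.104 SD: 1.10 SD gives 79.7% and 1.11 SD gives 80.4%. For 10/30, 1.05 SD gives 80.0%.

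**4. Sensitivity to the number of responders.** With 37 patients, the detectable difference runs from 1.04 SD (11 responders) to 1.15 SD (8 responders). With 40, it runs from 1.02 SD (11) to 1.09 SD (9). At 1.00 SD every one of these splits stays below 80%.

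**The case against.** The plan is not silent on the two-group question. The 1.00 SD sentence in IV.C refers to any quantitative biomarker, which by its wording can include a change in a blood marker. Against that benchmark the shortfall is modest: 80% stated, against 76% at 40 patients or 72% at 37. Nor does the protocol anywhere claim that 0.46 SD is detectable between responders and non-responders; it names the paired test each time and introduces it in IV.C as giving a sense of power. Finally, this is a correlative study on whatever specimens are available. The sample is not set by the calculation, and no treatment or accrual decision depends on it.

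Much of this stands. The 21% to 23% power at 0.46 SD measures what a misreading would cost; it does not contradict a stated claim. The fairer comparison is 1.00 SD against 1.05 to 1.10 SD.

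It does not remove the point. The 1.00 SD sentence carries over the tissue group sizes and fails at both blood sizes. IV.D repeats the 0.46 SD figure as the reason for the blood sample size, without the hedge and without reference to the 1.00 SD sentence. Nothing in the appendix reconciles 37 with 40.

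**Conclusion.** The concern holds as an inconsistency; the arithmetic in the plan is right on its own inputs.

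The sample size conflict is real but small in effect: power for the paired test is 77.7% at 37 instead of 81.0% at 40, so the claim of at least 80% fails at the plan's own estimate.

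The larger fault is that the blood rationale in IV.D supports a different question from the primary blood objective. For the planned comparison the detectable difference is about 1.05 to 1.10 SD of the change, more than twice the 0.46 SD printed there and somewhat above the general 1.00 SD. The two-group figures depend on the assumed responder share, unpaired t-test and equal SDs. IV.C and IV.D also allow transformation or non-parametric tests, so these values illustrate the sensitivity and do not fix it. The point should be corrected, but it does not threaten the study.

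**What to change.** 1. State one blood sample size in IV.B, IV.C and both places in IV.D.
2. In IV.D, and wherever the blood figure is repeated, add the detectable responder versus non-responder difference in change at that size, with its assumptions. Suggested wording for 37: assuming about 24% responders and an unpaired two-sided 0.05 t-test on the change, 37 patients (9/28) give about 80% power for a difference of 1.10 SD of the change (1.04 to 1.15 SD for 11 to 8 responders). For 40 (10/30): 1.05 SD (1.02 to 1.09 SD for 11 to 9 responders). If the phrase "at least 80%" is kept for 9/28, use 1.11 SD.
3. Keep the paired figure, but say that it applies only to the overall pre/post change. If the size is 37, restate it as 0.48 SD.
4. As a minor clarification, tie the 1.00 SD sentence in IV.C to the 44-patient tissue set (11/33).

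The cost is wording only: no extra patients, assays or analyses. The stated sensitivity of the primary blood analysis becomes less favourable.
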